4.6.4.2 Treatment

The following procedures and assessments will be performed during the treatment period according to the Schedule of Events (Table 9-1):

- Monitor for AEs
- Record concomitant medications
- Perform a safety 12-lead ECG at 0 (pre-dose), 1h, and 6h timepoints. If scheduled for the same time, safety 12-lead ECGs will always be performed before vital sign measurement and blood sample collection
- Measure vital signs at 0 (pre-dose), 0.5h, 1h, and 6h timepoints (blood pressure, heart rate, respiratory rate, and oral body temperature). If vital signs are scheduled at the same time as another event, vital signs will be measured after the ECG, but before blood sample collection

- Administer study drug according to the randomization schedule following all other pre-dose examinations and specimen collection
- Collect PK blood samples (8 mL) at the timepoints specified in Section 4.1
- Perform nasal irritation assessment at 0 (pre-dose), 4.5, 10, 30, 60 and 240 minutes as described in Section 4.7.2.6

4.6.5 Washout

There will be two washout days (72h from dose to dose) between the treatment periods. The following procedures and assessments will be performed during washout period:

- Monitor for AEs
- Measure vital signs (blood pressure, heart rate, respiratory rate, and oral body temperature)

4.6.6 Discharge (or Early Termination)

The following procedures and assessments will be performed before the subject is discharged from the study or at early termination:

- Perform a serum pregnancy test (female subjects only)
- Record concomitant medications
- Monitor for AEs
- Perform alcohol and drug screening (amphetamines, barbiturates, benzodiazepines, cannabinoids, cocaine, alcohol, opiates, phencyclidine, propoxyphene, and methadone)
- Perform clinical laboratory tests (hematology, serum chemistry, and urinalysis)
- Measure vital signs (blood pressure, heart rate, respiratory rate, and oral body temperature)
- Perform a safety 12-lead ECG
- Perform a complete physical examination
- Measure weight
- Discharge subject from the study clinic after completion of all study procedures

4.7 Study Procedures

4.7.1 Pharmacokinetic Assessments

4.7.1.1 Pharmacokinetic Sample Collection

For this study, PK blood samples will be collected on Day 1 of each treatment period (i.e., dosing days). Blood samples will be collected by direct venipuncture or by inserting an IV catheter into the subject's forearm region. A single PK blood sample (8 mL) will be collected at the following timepoints within each period: 0 (i.e., immediately before dosing), 2, 4.5, 7, 10, 12.5, 15, 20, 30, 45, 60, 120, 180, 240, 360, and 720 minutes after dosing on Days 1, 4 and 7 (Table 9-1). The target time of the PK blood collection is considered the most critical. If the collection time is more than ± 0.5 minute from the scheduled time for the first 15 minutes of collections or more than ± 2 minutes from scheduled timepoints, thereafter, this will be considered a protocol deviation.

Each blood sample will be labeled with subject number, study number, study day, time point, event, and a barcode that matches that belonging to the subject.

4.7.1.2 Specimen Handling

The PK blood samples (8 mL each) will be collected into 10 mL tubes containing K2EDTA, inverted several times to mix the blood with the anticoagulant, and placed in an ice bath. Within 30 minutes of collection, the samples will be centrifuged for 10 minutes, at 3000 revolutions per minute, at 4°C, by a study team member.

The plasma will be separated using a disposable plastic pipette and approximately half of the plasma will be transferred into duplicate cryotube vials (2 mL polypropylene tubes) labeled as Aliquot A (primary) and Aliquot B (backup). The plasma samples will be appropriately labeled and stored frozen at -70°C or below until shipment. Temperature monitoring logs should be maintained and accessible for review by the study monitor.

The Aliquot A samples (primary) will be shipped first, on dry ice, to the bioanalytical laboratory specified by the sponsor for processing when requested by the sponsor. The Aliquot B samples (backup) will be held for a second shipment at a time after the completion of all Aliquot A sample shipment(s) and the timing of the Aliquot B shipment communicated by the sponsor. None of the PK blood samples will be stored at clinical facility for future use. De-identified samples may be stored by the sponsor for additional exploratory analyses.

Plasma concentrations of naloxone will be assayed using a validated liquid chromatography with tandem mass spectrometry method.

4.7.1.3 Pharmacokinetic Parameters

The following PK parameters will be determined for each subject:

Plasma

- Concentrations at specified times after the first dose
- Maximum concentration (observed peak drug concentration) (C_{max}) on the specified day

- AUC from time 0 extrapolated to infinity (AUC_{0-inf})
- AUC from time 0 to the sampling time corresponding to the last quantifiable concentration (C_{last}) (AUC_{0-t})
- Partial AUCs (pAUC) over time intervals of 0 to 7 (pAUC₀₋₇), 0-10 (pAUC₀₋₁₀), 0-12.5 (pAUC_{0-12.5}), 0-15 (pAUC₀₋₁₅), 0-20 (pAUC₀₋₂₀), and 0-30 (pAUC₀₋₃₀) minutes.
- Time at which C_{max} occurs (t_{max})
- Elimination rate constant (K_{el})
- Terminal half-life (t_{1/2})
- Apparent clearance (CL/F)

4.7.2 Safety Assessments

Safety will be evaluated in terms of AEs, clinical laboratory results (hematology, serum chemistry, and urinalysis), vital sign measurements (blood pressure, heart rate, respiratory rate, and oral body temperature), safety 12-lead ECG results, and physical examination findings.

An examination of the nasal passage will be conducted by a trained observer to evaluate evidence of irritation to the nasal mucosa. This nasal irritation assessment will be taken at the following timepoints during study drug administration 0 (pre-dose), 4.5, 10, 30, 60, 240 minutes.

4.7.2.1 Adverse Events

4.7.2.1.1 Adverse Event Definitions

An AE is defined as any untoward and/or unintended sign, including an abnormal clinical laboratory finding, symptom, or disease temporally associated with the use of a study drug, whether or not considered related to the study drug. Events or conditions that increase in frequency or severity during or as a consequence of use of a drug in human clinical trials will also be considered AEs.

A treatment-emergent adverse event (TEAE) is defined as an AE that begins after study drug administration.

An unexpected AE is any AE having a specificity or severity not consistent with the current investigator's brochure for the study drug(s).

A serious adverse event (SAE) is defined as any AE occurring at any dose that meets the following criteria:

- Results in death,
- Is life threatening,

- Requires hospitalization or prolongation of existing hospitalization,
- Results in persistent or significant disability or incapacity,
- Results in a congenital anomaly/birth defect due to exposure prior to conception or during pregnancy, or
- Is an important medical event that may not meet the previous criteria but, based upon appropriate medical judgment, jeopardizes the subject or requires medical or surgical intervention to prevent one of the outcomes listed previously.

4.7.2.1.2 Adverse Event Reporting

The recording of AEs will begin after the subject signs the informed consent form and will continue until discharge (or early termination). All AEs, whether serious or nonserious and whether or not related to the study drug, must be recorded in the eCRF. Study subjects will be instructed to warn study staff if he or she has any unexpected symptoms. In addition, all subjects will receive a reminder telephone call approximately 24 h before check-in.

Any SAE (whether expected or unexpected) must be entered into the eCRF system and reported by email to the sponsor or designee using the SAE Reporting Form within 24 h of the investigator or study clinic staff becoming aware of the event. It is the responsibility of the investigator to report all SAEs to the sponsor, to provide the most complete report possible, and to assess each SAE for its relationship to the study drug. The investigator is responsible for obtaining follow-up information on all SAEs and submitting follow-up SAE data. Any unexpected SAEs must be reported promptly to the investigator's IRB as per the IRB's requirements.

In the event of a fatal or life-threatening SAE, the sponsor will notify the appropriate FDA authorities within 7 calendar days of receipt of the report. The sponsor will follow all 7-day alert reports with a written report within 10 working days of receipt of the case. Serious AE cases that concern nonfatal, nonlife-threatening events that are unexpected and at least possibly related to the study drug will be submitted in writing to the FDA within 10 working days of receipt.

Furthermore, any AEs that are not expected, occur at a higher frequency, or would require modification of the study protocol and/or informed consent must be reported to the FDA within 10 working days.

AEs that are assessed by the investigator as possibly or probably related to the study drug will be followed until they resolve or stabilize. All SAEs will be followed until resolution.

4.7.2.1.3 Assessment of Severity

The investigator will assess the severity of each AE using the following scale:

- Mild: The subject is aware of the AE but is still able to perform all activities; minimal or no medical intervention or therapy is required.
- Moderate: The subject has to discontinue some activities due to the AE; minimal or no medical intervention or therapy is required.
- Severe: The subject is incapacitated by the AE and is unable to perform normal activities; significant medical intervention or therapy is required, and hospitalization is possible.

4.7.2.1.4 Assessment of Causality

The investigator will assess the causal relationship/relatedness of each AE to the study drug using the following scale:

- Not Related: Onset of the AE has no reasonable temporal relationship to administration of the study drug, a causal relationship to administration of the study drug is biologically implausible, or the event is attributed to an alternative etiology.
- Unlikely Related: Onset of the AE has a reasonable temporal relationship to study drug administration and although a causal relationship is unlikely, it is biologically plausible.
- Possibly Related: Onset of the AE has a strong temporal relationship to administration of the study drug, cannot be explained by the subject's clinical state or other factors, and a causal relationship is biologically plausible.
- Probably Related: Onset of the AE shows a distinct temporal relationship to administration of the study drug that cannot be explained by the subject's clinical state or other factors, the AE is a known reaction to the product or chemical group, or can be predicted by the product's pharmacology.

4.7.2.1.5 Pregnancy

A serum pregnancy test will be performed for female subjects at the timepoints presented in the Schedule of Events (Table 9-1). If a subject becomes pregnant while on the study, this should be reported immediately to the investigator and sponsor and the subject will be withdrawn from the study. The subject will be instructed to follow-up with his or her personal physician. All pregnancies are to be reported as an AE and followed for outcome.

4.7.2.2 Clinical Laboratory Tests

Clinical laboratory and diagnostic screening tests will be performed at the timepoints presented in the Schedule of Events (Table 9-1) and will be collected in accordance with acceptable laboratory procedures. Clinical laboratory testing will be performed by the clinical study contractor(s). The clinical laboratory tests that will be performed are presented in Table 4-3. Unused clinical laboratory test samples will not be stored for future use.

Table 4-3: Clinical Laboratory Tests & Diagnostic Screening Tests

Hematology	Serum Chemistry	Urinalysis
Hematocrit Hemoglobin Platelet count Red blood cell count White blood cell count (with automated differential)	Alanine aminotransferase Albumin Alkaline phosphatase Aspartate aminotransferase Bicarbonate Bilirubin (total, direct, and indirect) Blood urea nitrogen Calcium Chloride Creatinine (including calculated creatinine clearance – Cockcroft Gault) Glucose Lactate dehydrogenase Magnesium Phosphorus Potassium Sodium Total protein Uric acid	Appearance Bilirubin Blood Color Glucose Ketones Leukocyte esterase Microscopic examination: red blood cells, white blood cells, epithelial cells, bacteria, crystals, and casts (if present) Nitrite pH Protein Specific gravity Urobilinogen
Diagnostic Screening Tests:		
Serum	Urine	Other
Serology (human immunodeficiency virus Ag/Ab Combo 1/2, hepatitis C virus antibody, and hepatitis B surface antigen) Female Subjects Only Human chorionic gonadotropin (for pregnancy)	Drug screen including: amphetamines, barbiturates, benzodiazepines, cannabinoids, cocaine, alcohol, opiates, phencyclidine, propoxyphene, and methadone	SARS-CoV2 molecular test

4.7.2.3 Vital Sign Measurements

Vital signs (blood pressure, heart rate, respiratory rate, and oral body temperature) will be measured using an automated device on days presented in the Schedule of Events (Table 9-1). The subject should be in a supine position, if possible, for a minimum of 5 minutes before vital signs are measured.

4.7.2.4 Safety 12-lead Electrocardiograms

12-lead ECGs will be obtained with the subjects in the supine position for a minimum of 5 minutes before recording. ECGs will be overread by a physician. If an abnormality is observed, the subject will be instructed to follow-up with his or her personal physician.

4.7.2.5 Physical Examinations

A complete physical examination will be performed on the days presented in the Schedule of Events (Table 9-1).

The complete physical examination will include, but not be limited to, assessments of the head, eyes, ears, nose, throat, skin, thyroid, nervous system, respiratory system, cardiovascular system, abdomen (liver and spleen), lymph nodes, and extremities. Height, weight (without shoes and wearing the lightest possible clothing), and calculation of body mass index will be performed at Screening and check-out.

If a clinically significant abnormality is observed upon physical examination, the subject will be instructed to follow-up with his or her personal physician.

4.7.2.6 Nasal Irritation Assessment

Nasal irritation (erythema, edema, and erosion) will be evaluated by a trained observer during study drug administration at the following timepoints: 0 (pre-dose), 4.5, 10, 30, 60 and 240 minutes. If a PK sample corresponds to the nasal irritation assessment the nasal assessment will be performed after the PK sample is obtained.

Nasal Irritation Scale

- 1 - Inflamed mucosa, no bleeding
- 2 - Minor bleeding which stops within 1 minute
- 3 - Minor bleeding, taking 1-5 minutes to stop
- 4 - Substantial bleeding for 4-60 minutes, does not require medical intervention
- 5 - Ulcerated lesions, bleeding which requires medical intervention

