7.5.6 Nasal Irritation Score Analyses

Nasal Irritation Score is an examination of the nasal passage conducted by a trained observer to evaluate evidence of irritation to the nasal mucosa. These results will be summarized using descriptive statistics for all treatment groups.

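### The nasal irritation scale has no score for a normal nose and leaves some bleeding states without a grade, so the by-treatment summary rests on a coding rule nobody has written down

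*Protocol*

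**What the plan says.** Protocol 4.7.2.6 opens with what is to be examined: "Nasal irritation (erythema, edema, and erosion) will be evaluated by a trained observer during study drug administration". The examination times are "0 (pre-dose), 4.5, 10, 30, 60 and 240 minutes" in each of the three periods. Five grades follow:

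- Grade 1: "Inflamed mucosa, no bleeding"
- Grade 2: "Minor bleeding which stops within 1 minute"
- Grade 3: "Minor bleeding, taking 1-5 minutes to stop"
- Grade 4: "Substantial bleeding for 4-60 minutes, does not require medical intervention"
- Grade 5: "Ulcerated lesions, bleeding which requires medical intervention"

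Protocol 4.9.7.6 gives the score a by-treatment purpose: it is meant to show how much irritation each treatment causes. The analysis in SAP 7.5.6 is one sentence: "These results will be summarized using descriptive statistics for all treatment groups". Neither document names the statistics, restates the scale or says how a normal examination is recorded. Protocol 4.9.8 says that missing data are not imputed.

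**The concern.** An ordinal scale needs a place for every state the observer can meet, and only one place for each. This one has no place for the commonest state expected. The subjects are healthy volunteers, and those with a recent nosebleed, a recent upper respiratory infection or current congestion are excluded, so a normal nose is the expected pre-dose result and a likely result at many later times.

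Treatments A and B each put two sprays into each nostril, while treatment C puts in one. The score is the only nasal examination scheduled after dosing within each period, so it is the natural place to look for extra irritation from re-dosing. If normal noses are left blank, or placed in the lowest grade for want of another, a summary of scores could hide a difference in how many subjects were irritated. The study is unblinded, and the choice would be made at the bedside or in programming without a written rule.

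**Working it through.** There is no stated figure to reproduce. The check has three parts.

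**1. Number of examinations.** Inputs: about 20 subjects (Protocol 4.2), three periods (4.1), six times per period including pre-dose (4.7.2.6).

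- All examinations: 20 x 3 x 6 = 360.
- Pre-dose examinations: 20 x 3 = 60.

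**2. Mapping states to grades.** Each state is compared with the five definitions, assuming no medical intervention is needed.

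| State | Grade |
|---|---|
| Normal mucosa | none |
| Inflamed, no bleeding | 1 |
| Minor bleeding, under 1 min | 2 |
| Minor bleeding, exactly 1 min | 2 and 3 |
| Minor bleeding, over 1 and up to 5 min | 3 |
| Minor bleeding, over 5 min | none |
| Substantial bleeding, under 4 min | none |
| Substantial bleeding, 4 to 60 min | 4 |
| Substantial bleeding, over 60 min | none |

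On duration alone, a bleed of 4 to 5 minutes fits both grade 3 and grade 4. Once the amount of bleeding is applied, each such bleed has one grade, but the documents do not define the two words that do the separating. Edema and erosion are on the list of signs to be evaluated, yet no grade names either. Ulceration without bleeding has no clear grade.

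**3. How the coding of a normal nose moves a summary score.** The counts are assumed, because the documents give no incidence. At one time point, 2 of 20 subjects are at grade 1 on one treatment and 10 of 20 on another; the rest are normal.

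- Normal coded 0: (2 x 1 + 18 x 0)/20 = 0.10 and (10 x 1 + 10 x 0)/20 = 0.50; difference 0.40.
- Normal left blank and not imputed: 2/2 = 1.0 and 10/10 = 1.0; difference 0.
- Normal coded 1: 20/20 = 1.0 and 20/20 = 1.0; difference 0.

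Reported instead as a proportion of subjects examined, the same data read 2/20 = 10% and 10/20 = 50%. That result does not depend on whether normal is called 0 or left ungraded, provided the denominator is everyone examined and normal noses are not counted in grade 1.

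**The case against.** The case on the other side has four parts.

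*Grades 3 and 4 do not overlap.* One is for minor and the other for substantial bleeding, so a 4.5-minute bleed takes one grade or the other according to amount. This stands. A reader might infer that the two grades classify the same bleed twice; the text does not support that. What is left is that the separating words are undefined.

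*Local tolerability is captured elsewhere.* A reader might take the score to be the only such measure. It is not. Adverse events are all recorded, graded for severity and summarized by treatment at onset (Protocol 4.7.2.1.2, 4.7.2.1.3 and 4.9.7.1; SAP 7.5.1), and the label reactions listed in Protocol 4.1.1 include several nasal ones. The physical examination covers the nose and is repeated at discharge, with abnormal findings recorded as adverse events. A notable nosebleed would therefore still be reported. This stands too, although SAP 7.5.5 notes that the physical examination is not planned for each period, so it cannot replace the repeated post-dose score.

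*No mean and no formal comparison is prescribed.* SAP 7.5.2 and 7.5.3 list the mean for laboratory tests and vital signs; SAP 7.5.6 does not. This stands, so the example above shows what could happen under an unstated choice, not an error in a planned statistic. But the plan does not specify counts per grade either.

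*Absence of irritation would naturally be recorded as none.* Scoring a normal nose as 1 would contradict the grade's own definition, and the eCRF may offer a response for no finding. That is plausible, and it makes the coding as 1 the less likely route. It remains a convention that neither document states, and it does nothing for the ungraded bleeding states.

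**Conclusion.** The point holds as a defect in the scale, with limited consequences. The missing score for a normal nose matters most: it affects the expected result at 60 pre-dose examinations and probably many of the other 300. The bleeding gaps concern states likely to be rare.

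The impact stops at a descriptive safety summary. A reader might infer that a planned treatment comparison is invalid. The documents plan no formal comparison of this score, and the primary, secondary and exploratory endpoints and the sample size do not depend on it.

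The conclusion assumes that the five listed grades are the whole scale and that no eCRF instruction already supplies a code for normal mucosa; the eCRF and data management plan are not part of the documents. The 0.10, 0.50 and 1.0 figures rest on assumed counts and show direction only.

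**What to change.** Before first dosing:

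1. Add a grade 0 for normal mucosa with no irritation to Protocol 4.7.2.6 and the eCRF.
2. Define *minor* and *substantial*, and reconcile the duration bands so that every bleeding state has exactly one grade, including a bleed of exactly 1 minute. State where edema, erosion and ulceration without bleeding belong.
3. In SAP 7.5.6, report the number and percentage of examined subjects in each grade, including 0, by treatment and time point, with the pre-dose grade shown.

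The cost is a short wording change to the protocol and eCRF and one or two sentences in the SAP. No examination is added, and no dose, schedule or clinical management changes. Timing matters, because an ambiguous bedside entry may not be recoverable later.

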4.7.3 Demographics and Medical History

Demographic data (date of birth, gender, race, and ethnicity) will be collected at Screening. Each subject will provide a complete medical history at Screening that will be reviewed at check-in. Specific information relating to any prior or existing medical conditions/surgical procedures will be recorded in the subject's eCRF.

4.8 Study Treatments

4.8.1 Treatments Administered and Schedule

Subjects will receive each of the following treatments (Table 4-4) according to the randomization schedule. Drug administration will occur on Day 1, 4 and 7 with a 2 day washout period in between.

Table 4-4: Study Treatments and Dose Schedule

Treatment	Description	Dose Schedule
A	4 doses of 4 mg IN naloxone doses	1 dose every 2.5 min; L at 0 min, R at 2.5 min, L at 5 min, R at 7.5 min
B	4 doses of 4 mg IN naloxone doses	2 doses every 2.5 min; L and R at 0* min, L and R at 2.5* min
C	2 doses of 4 mg IN naloxone doses	L at 0 min, R at 2.5 min

*L = Left Nostril, R = Right Nostril, * doses will be ~5 seconds apart (one after the other)*

Subjects will be randomized to one of six treatment sequences (i.e., ABC, ACB, BAC, BCA, CAB, CBA). Study drug will be administered by a clinical research nurse on the study clinic floor at the subject's bedside. The pharmacist and investigator will be available if needed during study drug administration. The subject should remain fully supine for approximately one hour post-dose. Subjects should be instructed not to breathe through the nose during administration of the nasal spray into the nose. Subjects will be instructed to leave their masks off for twenty minutes after drug administration.

IN naloxone doses will be administered as a 4 mg IN spray at the times specified above. No treatments will include placebo.

